11.4 Planned Subgroups and Covariates

All patients enrolled in the study, except patients whose device is damaged in a subsequent procedure prior to reaching the primary efficacy endpoint, will be included for the primary analyses. If warranted, baseline characteristics (including but not limited to: patient demographics and hernia type) and procedural details (including but not limited to: procedure type (laparoscopic or open), surgical repair technique, fascial closure, and location of device placement) will be analyzed to determine their impact on the hernia recurrence rate.

11.5 Missing Data

The total study enrollment is augmented to achieve sufficient data to analyze the study outcome in the presence of missing data due to lost to follow-up or withdrawn patients. However, it is also recognized that patients may refuse or be unable to return to the study

site for a physical exam at the 1-year and 2-year timepoints, leading to missing physical exam information.

The primary endpoint will be analyzed using per-protocol and analyzable patient populations to assess the robustness of the efficacy results. Three imputation methods will be implemented for missing physical exam data to evaluate the impact of missing data on the conclusions of treatment effect: (1) complete case analysis, (2) estimating missing data with the best available data, (3) multiple imputation. All three methods for missing data will be used to assess the robustness of the primary endpoint.

Analyses will account for missing data in the following manner: if missing data can be determined from a subset of best available data, these data will be documented and analyzed. Multiple imputation will be considered, and appropriate methods to impute data based on the analysis population will be documented and presented in the analysis results.

Specifically, when dealing with missing physical exam information for the primary recurrence endpoint, the following analysis is planned:

1. Patients self-reporting the absence of recurrence symptoms will be deemed to not have experienced a hernia recurrence in the absence of physical exam/imaging information.
2. Data from patients with both physical exam/imaging information and positive recurrence symptoms on the self-assessment will be utilized to assess the accuracy of patient self-reporting of hernia recurrence.
3. This level of accuracy will be applied to the patient subset with only positive recurrence symptoms on the self-assessment as a means of estimating the true recurrence rate.

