9.4 Follow-up

Patients are expected to participate in this study for 2 years after the procedure. The follow-up visits will occur within the time frames listed below. Following the study procedure, assessments will be completed as described in Table 9.4-1.

Table 9.4-1. Follow-up requirements

30-day Follow-up (± 15 days)	
Timing	15-45 days following the study procedure
Type	In person
Assessments	Physical exam of the incision and abdominal wall
	Record specific data points within the EDC system
	Administer a postoperative assessment (patient questionnaire)
6- month Follow-up (± 30 days)	
Timing	153-213 days following the study procedure
Type	In person
Assessments	Physical exam of the incision and abdominal wall
	Record specific data points within the EDC system
	Administer postoperative assessment (patient questionnaire)
1-Year Follow-up (± 90 days)	
Timing	275 – 455 days following the study procedure
Type	In person ¹
Assessments	Physical exam of the incision and abdominal wall
	Record specific data points within the EDC system
	Administer postoperative assessment (patient questionnaire)
2-Year Follow-up (± 90 days)	
Timing	640 – 820 days following the study procedure
Type	In person ¹
Assessments	Physical exam of the incision and abdominal wall
	Record specific data points within the EDC system
	Administer postoperative assessment (patient questionnaire)

¹For the 1 and 2-year follow-up visits: Every attempt should be made to have the patient return for a physical exam at the 1-year and 2-year timepoints in order to determine hernia recurrence. Results from a physical exam made by a non-study physician (e.g. primary care physician) can be included if assessment at the clinical site is not possible.

If the patient refuses or is unable to return in person for the 1-year or 2-year physical exam, patient self-assessment of the presence of recurrence symptoms, patient responses regarding adverse events,

and patient questionnaires may be obtained from the patient via telephone or email. If the patient self-assessment of the presence of recurrence symptoms suggests that a hernia is present, the patient should be contacted and requested to return for a physical exam for confirmation.

Patient reported outcomes will be tabulated and reported. The primary endpoint will be analysed as noted in Section 11.0.

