APPENDIX C: Definitions

Center of Disease Control (CDC) Wound Classification:

Classification	Description
Clean (Class I)	An uninfected operative wound in which no inflammation is encountered and the respiratory, alimentary, genital, or uninfected urinary tract is not entered. In addition, clean wounds are primarily closed and, if necessary, drained with closed drainage. Operative incisional wounds that follow non-penetrating (blunt) trauma should be included in this category if they meet the criteria.
Clean-contaminated (Class II)	An operative wound in which the respiratory, alimentary, genital, or urinary tract are entered under controlled conditions and without unusual contamination. Specifically, operations including the biliary tract, appendix, vagina, and oropharynx are included in this category provided no evidence of infection or major break in sterile technique is encountered.
Contaminated (Class III)	Open, fresh, accidental wounds. In addition, operations with a major break in sterile technique (e.g., open cardiac massage) or gross spillage from the gastrointestinal tract, and incisions in which acute nonpurulent inflammation is encountered are included in this category.
Dirty-infected (Class IV)	Old traumatic wounds with retained devitalized tissue and those that involve existing clinical infection or perforated viscera. This definition suggests that the organisms causing post-operative infection were present in the operative field before the operation.

Hernia Recurrence (recurrence of tissue defect):

Any of the following post-operative findings at the site of the hernia defect repaired at the index procedure will be categorized as a hernia recurrence:

- A symptomatic, palpable or visible protrusion of underlying tissue through a defect in the abdominal wall, possibly with a palpable fascial defect

Any patient who presents asymptotically, but additional imaging indicates presence of a hernia.

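### Section 11.5 counts every unexamined, symptom-free patient as recurrence-free and never corrects for missed recurrences, so the best-available-data estimate leans in the device's favour by an unknown amount.

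*Combined protocol and SAP*

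**What the plan says.** The primary endpoint is hernia recurrence through 1 year (Section 7.5.1), and Table 7.6-1 gives clinical examination as its assessment. The 30-day and 6-month visits are in person. At 1 and 2 years a patient who cannot or will not attend may instead report symptoms by telephone or email, and an examination by a non-study physician is also accepted (Section 9.4).

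Section 11.5 lists three approaches to missing examination data: complete case analysis, best available data and multiple imputation. It says that all three will be used, and names none as primary. Only one procedure is then set out in steps, introduced by "when dealing with missing physical exam information for the primary recurrence endpoint, the following analysis is planned". Its three parts are these:

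1. On negative reports, the rule reads: "Patients self-reporting the absence of recurrence symptoms will be deemed to not have experienced a hernia recurrence in the absence of physical exam/imaging information".
2. The accuracy of self-report is taken from "Data from patients with both physical exam/imaging information and positive recurrence symptoms on the self-assessment".
3. "This level of accuracy will be applied to the patient subset with only positive recurrence symptoms on the self-assessment".

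Two other places bear on this. Section 9.4 provides for recall only after a positive report: "If the patient self-assessment of the presence of recurrence symptoms suggests that a hernia is present, the patient should be contacted" and asked to come in for confirmation. Appendix C includes as a recurrence "Any patient who presents asymptotically, but additional imaging indicates presence of a hernia"; the adverb is evidently meant as asymptomatically.

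**The concern.** The procedure treats the two kinds of self-report differently. A positive report is weighted by the observed proportion of positive reports that examination confirms, which is a positive predictive value (PPV). A negative report is taken as certain. Since Appendix C allows a recurrence without symptoms, absence of symptoms cannot establish absence of the endpoint. Because only symptom-positive patients are asked back, missed recurrences are neither looked for nor estimated.

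The resulting error has one direction: recurrences among unexamined, symptom-free patients are set to zero, which lowers the recurrence rate and favours the device. It grows with the share of patients followed remotely. The expected recurrence rate (19.9%) lies only 2.1 points below the threshold in Section 11.3 (22%), so even a modest error could matter to the conclusion.

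**Working it through.** **Inputs from the documents.** Expected success is 80.1%, so expected recurrence is 100 - 80.1 = 19.9% (Section 11.1). The null hypothesis is recurrence of at least 22% (Section 11.3), so the gap is 22 - 19.9 = 2.1 points. There are 86 evaluable patients, α = 0.05 and a two-sided interval (Section 11.1). The plan gives no figure for misclassification, so there is none to reproduce.

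**Inputs assumed, because the documents do not give them.**
- u, the share of patients with self-report only at 1 year: 10%, 20%, 30%.
- s, the probability that a patient with a recurrence reports symptoms: 0.9, 0.7, 0.5.
- e, the share of recurrences already found at the 30-day or 6-month examination: 0 or one half. The endpoint is cumulative, so these stay counted whatever the patient later says by telephone.

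**Formula.** Let π be the true recurrence rate. If the PPV applied in step 3 is correct, symptom-positive patients contribute the right number of recurrences on average. The only loss is among unexamined, symptom-negative patients:

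expected estimate = π × [1 - u(1 - s)(1 - e)], so bias = -π × u(1 - s)(1 - e).

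The bias is zero only if u = 0, s = 1 or e = 1. Example at π = 19.9%, u = 20%, s = 0.5: with e = 0, 0.199 × 0.2 × 0.5 = 1.99 points; with e = 0.5, half of that, 1.0 point.

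**Effect on the conclusion.** The plan does not spell out a pass rule beyond the hypothesis and a 95% interval. I take a pass to mean that the upper exact 95% limit lies below 22%. With n = 86 and true rate 22%, P(X ≤ 11) = 0.0219 and P(X ≤ 12) = 0.0422. Only the first is below 0.025, so a pass needs at most 11 recurrences. The pass probability under the rule is P(X ≤ 11) with n = 86 and rate 0.22 × [1 - u(1 - s)(1 - e)].

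| u | s | Bias in points at 19.9%, e = 0 | Same, e = 0.5 | Pass probability at true 22%, e = 0 | Same, e = 0.5 |
|---|---|---|---|---|---|
| 10% | 0.9 | 0.2 | 0.1 | 2.4% | 2.3% |
| 10% | 0.7 | 0.6 | 0.3 | 3.0% | 2.6% |
| 10% | 0.5 | 1.0 | 0.5 | 3.8% | 2.9% |
| 20% | 0.9 | 0.4 | 0.2 | 2.7% | 2.4% |
| 20% | 0.7 | 1.2 | 0.6 | 4.2% | 3.0% |
| 20% | 0.5 | 2.0 | 1.0 | 6.2% | 3.8% |
| 30% | 0.9 | 0.6 | 0.3 | 3.0% | 2.6% |
| 30% | 0.7 | 1.8 | 0.9 | 5.6% | 3.6% |
| 30% | 0.5 | 3.0 | 1.5 | 9.9% | 4.8% |

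Bias is downward throughout. Without misclassification the pass probability is 2.2%. In patients, u = 20% and s = 0.5 with e = 0 means 86 × 0.2 × 0.199 × 0.5 = 1.7 missed recurrences.

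**Does a symmetric correction remove the bias?** Take π = 22%, s = 0.7, u = 20%, e = 0 and an assumed specificity of 0.9. The probability of a positive report is 0.22 × 0.7 + 0.78 × 0.1 = 0.232. Then PPV = 0.154/0.232 = 0.664, and the recurrence risk after a negative report (1 - NPV, where NPV is the negative predictive value) is 0.066/0.768 = 0.086. The planned rule gives 20.7%. Giving negative reports a risk of 0.086 instead of 0 restores 22.0%.

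**The case against.** The strongest reply is that the plan does not rely on this rule alone. Complete case analysis does not use it and multiple imputation need not, so disagreement between the three would show the problem. That stands in part. It means the bias belongs to the best-available-data analysis, and a reader who infers that the trial's primary result is necessarily biased goes further than the text. But no method is named as primary, and this is the only one set out in steps for the primary endpoint. The section also weakens its commitment to multiple imputation, saying later only that it will be considered.

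The second reply is that the size may be small. This stands. In-person examinations at 30 days and 6 months will already have caught some recurrences, and outside examinations shrink the self-report-only group. At a sensitivity of 0.9 the bias is at most 0.6 points even with no earlier detection.

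The third is that step 3 could push the other way. A reader might infer that both adjustments lower the rate; they do not. Weighting positive reports by a correct PPV is unbiased, and if patients who return are more often true recurrences, the PPV is too high and raises the estimate. Full cancellation is demanding, however. In the worked example, with no phoned positive patient returning, it needs an applied PPV of 0.22/0.232 = 0.95 against a true 0.66. At s = 0.5 it would need a PPV above 1.

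A reader might also infer that the interval is too narrow because the PPV comes from few patients and is treated as known. The documents state neither the number of such patients nor how the uncertainty will be handled, so that is not established.

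**Conclusion.** The asymmetry is in the text, and its direction follows from it. The best-available-data estimate of 1-year recurrence is biased downward, in the device's favour, whenever self-report misses recurrences not already found at an earlier visit. This assumes that the PPV from returning patients holds for those who do not return.

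The size is not known. Under the assumed ranges it is about 0.2-3.0 points with no earlier detection and about 0.1-1.5 points if half of recurrences are found earlier. The probability that a device truly at 22% passes rises from 2.2% to between 2.3% and 9.9%. It is tempting to say that the bias consumes the whole 2.1-point gap. That takes roughly 20% remote follow-up, a sensitivity of 0.5 and no earlier detection, and the documents support none of these figures. The case for changing the rule rests on its direction, on its place in the primary endpoint and on the low cost of repair.

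**What to change.** 1. Do not use the first rule of Section 11.5 for the primary estimate. Name multiple imputation as the primary method, and treat the recurrence status of unexamined, symptom-negative patients as missing. Impute it from baseline data, earlier examinations and self-report, so that the uncertainty reaches the interval. State the imputation model in advance. Where self-report and examination are not both observed, the effect of a negative report must enter as a stated assumption.
2. Keep the present rule, labelled as the best case, among the sensitivity analyses.
3. Add a worst-case analysis and a tipping-point analysis: raise the number of these patients counted as recurrences from none to all, and report where the conclusion against 22% changes. This needs no new data.
4. Optionally, for patients who have not yet reached the 1-year visit, ask the same symptom question before the examination. Negative and positive reports can then both be checked, and 1 - NPV and PPV can inform the imputation.

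Items 1 to 3 are changes to analysis wording. Item 4 changes the protocol and patient materials, which needs IRB approval (Section 15.1), and cannot be recovered for patients already past the visit. It also assumes that NPV carries over to patients who do not attend. Because Appendix B schedules no imaging, it would still miss hernias visible only on imaging. The price overall is a slightly higher recurrence estimate and a wider interval.

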7.6 Variables to be Measured to Demonstrate Achievement of Endpoints

The endpoints and measures will be assessed as described in Table 7.6-1.

Table 7.6-1. Assessment of Endpoints and Measures

Endpoint / Measure	Assessment ¹
Hernia recurrence	Clinical examination
Rate of adverse events	Evaluation based upon reports of events submitted by the study sites
Rate of Surgical Site Occurrences (SSO)	Evaluation based upon reports of occurrences submitted by the study sites
Rate of Surgical Site Occurrences needing Intervention (SSOPI)	Evaluation based upon reports of occurrences submitted by the study sites

Patient quality of life	Postoperative assessment (patient questionnaire)
-------------------------	--

¹For the 1 and 2-year follow-up visits: Every attempt should be made to have the patient return for a physical exam at the 1-year and 2-year timepoints in order to determine hernia recurrence. Results from a physical exam made by a non-study physician (e.g. primary care physician) can be included if assessment at the clinical site is not possible.

If the patient refuses or is unable to return in person for the 1-year or 2-year physical exam, patient self-assessment of the presence of recurrence symptoms, patient responses regarding adverse events, and patient questionnaires may be obtained via telephone or email. If the patient self-assessment of the presence of recurrence symptoms suggests that a hernia is present, the patient should be contacted and requested to return for a physical exam for confirmation.

Patient reported outcomes will be tabulated and reported. The primary endpoint will be analysed as noted in Section 11.0.

Patient data will be documented by trained personnel at the clinical site and recorded onto eCRFs through an electronic data capturing (EDC) system. The assessment schedule is summarized in Table 7.6-2 and in Appendix B:

Table 7.6-2. Assessment schedule

	Pre-Procedure	Procedure	Follow-up			
			30 days (± 15 days)	6 month (± 30 days)	1 year (± 90 days)	2 years (± 90 days)
Consent	X					
Medical history	X					
Procedure Information		X				
Physical exam	X	X	X	X	X	X
Patient Reported Outcomes measures			X	X	X ^a	X ^a
Adverse events		X	X	X	X ^a	X ^a

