APPENDIX B: Study Event Schedule

	Pre-Procedure	Procedure	Follow-up			
			30 days (± 15 days)	6 months (± 30 days)	12 months (± 90 days)	2 years (± 90 days)
Informed consent	X					
Medical history	X					
Procedure Information		X				
Physical exam	X	X	X	X	X ¹	X ¹
Patient Reported Outcomes measures			X	X	X ¹	X ¹
Adverse events		X	X	X	X ¹	X ¹

¹Every attempt should be made to have the patient return for a physical exam at the 1-year and 2-year timepoints in order to determine hernia recurrence. Results from a physical exam made by a non-study physician (e.g. primary care physician) can be included if assessment at the clinical site is not possible. If the patient refuses or is unable to return in person for the 1-year or 2-year physical exam, patient self-assessment of the presence of recurrence symptoms, patient responses regarding adverse events, and patient questionnaires may be obtained via telephone or email.

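### Section 11.5 calibrates positive recurrence self-reports on patients who also have an exam or imaging, but the schedule does not provide for the self-assessment in patients who attend, so the calibration set is likely to be very small and self-selected.

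*Combined protocol and SAP*

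**What the plan says.** Section 11.5 gives a three-step rule for the primary recurrence endpoint when the physical exam is missing. Step 1 counts patients who report no symptoms as free of recurrence. Step 2 builds a calibration: "Data from patients with both physical exam/imaging information and positive recurrence symptoms on the self-assessment will be utilized" to judge how accurate self-report is. Step 3 uses it: "This level of accuracy will be applied to the patient subset with only positive recurrence symptoms on the self-assessment".

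The recurrence self-assessment is otherwise mentioned only in the notes to Tables 7.6-1, 7.6-2 and 9.4-1 and to Appendix B, always under the same condition. Section 7.6 reads: "If the patient refuses or is unable to return in person for the 1-year or 2-year physical exam, patient self-assessment". Appendix B continues: "patient self-assessment of the presence of recurrence symptoms, patient responses regarding adverse events, and patient questionnaires may be obtained via telephone or email". Sections 7.6 and 9.4 add that when the self-assessment suggests a hernia, "the patient should be contacted and requested to return for a physical exam for confirmation".

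For patients who attend, Table 9.4-1 lists a physical exam, EDC data points and "Administer postoperative assessment (patient questionnaire"). Neither Table 7.6-2 nor Appendix B has a row for the self-assessment.

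**The concern.** Step 2 needs two measurements on the same patient, a symptom self-report and an exam or scan. The natural source is the large group who attend the visit, but the plan does not say that they complete the self-assessment. The notes list it separately from the questionnaires, and Section 7.5.3 says that the patient-reported outcomes serve to evaluate function and pain independently of recurrence. The main stated route to a pair is therefore recall: a remote patient reports symptoms, is asked to come in, and does.

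Two problems follow. The set is likely to be very small, so the accuracy figure is close to uninformative and may have no data behind it. It is also self-selected: it describes symptomatic patients who agreed to return and is applied to symptomatic patients who did not. At stake is one of the three analyses that Section 11.5 uses to judge how robust the primary result is.

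**Working it through.** The plan states no expected size for the calibration set and no rates of non-attendance, symptoms or return, so there is no planned figure to reproduce. The only input from the documents is the enrolment of 95 (Section 11.1). The rest are assumptions, shown as ranges:

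- r, share remote at 1 year: 10-30%
- s, share of remote patients reporting symptoms: 15-25%
- q, share of those who return when recalled: 50-75%

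**Pairs from recall** = 95 × r × s × q.

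- Low: 95 × 0.10 × 0.15 × 0.50 = 0.7
- Middle: 95 × 0.20 × 0.20 × 0.625 = 2.4
- High: 95 × 0.30 × 0.25 × 0.75 = 5.3

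With a Poisson approximation, the chance of no pair at all is exp(-0.71) = 49% at the low end and exp(-2.375) = 9% in the middle.

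**Precision of the accuracy figure** (Clopper-Pearson 95% interval for the share of positive self-reports that are confirmed):

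- 1 of 2: 1% to 99%
- 2 of 3: 9% to 99%
- 4 of 5: 28% to 99%

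A wider set of assumptions changes little. Let s = 0.199 × sensitivity + 0.801 × (1 - specificity), using the recurrence of 19.9% implied by Section 11.1 (1 - 80.1%). With 40% remote, sensitivity 0.9, specificity 0.7 and 80% returning, s = 0.179 + 0.240 = 0.419, and the pairs number 95 × 0.40 × 0.419 × 0.80 = 12.7. That is the largest value over the combinations tried. Even 5 of 8 gives 24% to 91%.

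**Patients to whom the figure is applied** = 95 × r × s × (1 - q).

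- Low: 95 × 0.10 × 0.15 × 0.25 = 0.4
- Middle: 95 × 0.20 × 0.20 × 0.375 = 1.4
- High: 95 × 0.30 × 0.25 × 0.50 = 3.6

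The largest possible effect on the recurrence rate comes from moving the accuracy from 0% to 100%. It is 1.4/95 = 1.5 points in the middle and 3.6/95 = 3.75, or about 4, points at the extreme.

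**If attending patients also completed the self-assessment**, the symptom-positive patients with an exam would number 95 × (1 - r) × s, from 95 × 0.70 × 0.15 = 10 to 95 × 0.90 × 0.25 = 21, taking the same symptom range for attenders. For example, 12 of 18 gives 41% to 87%: still wide, but usable.

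**The case against.** The strongest reply is that exclusivity is inferred from silence. The notes permit a remote mode. Two of the three items they list, adverse events and questionnaires, are also collected from attenders, so being in that list does not make an item remote-only. Section 13.0 treats the telephone as one way among others of obtaining hernia symptoms. Appendix C defines recurrence partly by symptoms, which sites may therefore record at the exam. The eCRF and questionnaire are not shown. This stands: a reader might infer that attenders are never asked, and the documents do not establish that. They show that the schedule does not provide for it.

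Recall is also not the only source of pairs. The plan accepts exams by non-study physicians, step 2 accepts imaging, and step 2 is not confined to the 1-year contact. These can add some pairs, so 1 to 5 counts recall at 1 year only.

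A reader might further infer that the primary result hangs on one or two patients, because the assumed 19.9% lies 2.1 points, about two of 95 patients, below the 22% boundary in Section 11.3. That compares a point estimate with a threshold, whereas Section 11.2 reports a 95% confidence interval. At 19 of 95 the Wilson upper limit is about 29%, already well above 22%, and at 17 of 95 it is still about 27%. Two patients would not change that conclusion. Complete-case analysis and multiple imputation are planned as well.

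Finally, attenders also differ from non-attenders, so the proposed change does not remove selection. That is right, and it has to be stated as an assumption.

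**Conclusion.** The point holds as a gap between the analysis rule and the data collection. Section 11.5 needs paired measurements that the schedule does not provide for in the patients best placed to supply them. If no existing item fills the gap, the accuracy of positive self-reports would rest mainly on a handful of recalled patients. It would be very imprecise, and it would be carried over to patients who differ in exactly the respect that put them in the other group.

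The consequence for the primary rate is modest and limited to the best-available-data analysis. The counts of pairs and of corrected patients rest on assumed rates, and the conclusion lapses if the questionnaire or eCRF already records recurrence symptoms at attended visits. The change is still worth making: it is cheap, and a self-report made before the exam cannot be recovered once the visit has passed.

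**What to change.** - In Table 7.6-2, Table 9.4-1 and Appendix B, add the recurrence-symptom self-assessment for all patients at the 1-year and 2-year visits. Those who attend complete it before the exam, so that the finding cannot influence the answer. If such an item already exists, name it in the schedule and in Section 11.5 instead.
- In Section 11.5 step 2, estimate accuracy from all patients with both measurements, for negative as well as positive self-reports. This also makes the step 1 rule checkable.
- Carry the uncertainty of the accuracy estimate into the confidence interval for the recurrence rate, rather than treating it as known.
- State as an assumption that self-report is equally accurate in patients who attend and those who do not.

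The cost is a short form at two visits that already include a questionnaire, with wording changes to the schedule and Section 11.5. No extra visit is needed, and the added patient burden is small.
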